Protocol Title:
Treating Bacterial Overgrowth in Parkinson's Disease

Principle Investigator: [name]
Co-Investigator: [name]

Amendment 3

HYPOTHESIS AND SPECIFIC AIMS

Parkinson's disease (PD) is a progressive neurodegenerative disorder that includes motor and non-motor impairment, including gastrointestinal (GI) dysfunction, one of the earliest abnormalities. The GI dysfunction is expressed as reduction of intestinal motility, which puts PD patients at risk for developing small intestinal bacterial overgrowth (SIBO), which develops in about 50% of PD patients, compared to only 8-20% of healthy age-matched controls[1, 2]. SIBO-positive PD patients have poorer response to therapy and more motor fluctuations than non-SIBO PD patients. Finally, open-label data suggest that the antibiotic rifaximin leads to eradication of SIBO and improvement in motor control in affected PD patients.

Here we propose to collect pilot data that would support the submission of a U01 application to the NIH for a large randomized controlled trial investigating the effect of SIBO eradication on reducing motor complications in PD patients. **Our central hypothesis is that SIBO-positive PD patients treated with rifaximin will exhibit an improvement in motor fluctuations as measured by a decrease in daily “off” time.**

Primary endpoints: to determine the change in “off” time after rifaximin treatment as measured by both patient report (the Hauser PD diary) and an objective monitoring system (Kinesia 360). “Off” time will be compared using a between-subjects analysis (rifaximin versus placebo), as well as a within-subjects analysis comparing each subject's baseline to 1 and 3 months post-rifaximin treatment. Examining 2 post-treatment time points will provide an estimate for the optimal time point for the primary outcome measure as well as for treatment duration in a future study.

Secondary endpoints:

1. **to investigate whether the treatment effect of rifaximin varies by method of SIBO detection.** We propose to use two non-invasive methods of SIBO detection, serum unconjugated bile acids versus a combination of lactulose and glucose breath tests. Thus, we can determine if there is a differential treatment effect based on method of detection, and use these data to select the detection method for a larger, randomized trial.

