Our primary outcome, change in “off” time, will be analyzed using two separate analyses. A within-subjects comparison (paired t-test) will compare all subjects (n=24) before and after rifaximin treatment, whereas a between-subjects analysis (two-sample t-test) will compare placebo treatment (n=12) to rifaximin treatment (n=12). Therefore, we will have one analysis with greater power to detect a treatment effect, and a second analysis with greater validity for designing a future placebo-controlled trial.

Based on previous data, we have estimated that SIBO-positive PD patients have 5.1 hours of “off” time, with a treatment effect of rifaximin to decrease “off” time by 2 hours. Standard deviation is estimated to be approximately 1.5 to 2 hours [2].

Because all subjects will ultimately receive rifaximin treatment, a within-subjects analysis will compare all 24 subjects before and (1 and 3 months) after treatment using paired t-tests. For group A, this corresponds to baseline versus 1 month, and baseline versus 3 months. For group B, this corresponds to 3 months (end of placebo treatment, and baseline for rifaximin treatment) versus 4 months, and 3 months versus 6 months. Assuming a mean “off” time before treatment of 5.1 hours, a conservative estimate of standard deviation of 2.5 hours, and a moderate correlation of 0.7 between the measurements before and after treatment, we will have 99.8% power to detect a difference of 2 hours, and 95.3% power to detect a difference of 1.5 hours of “off” time.

A second analysis will compare placebo treatment versus rifaximin treatment between subjects. We will use a two-sample t-test to compare the “off” time between groups A and B at 1 month and 3 months past baseline. Assuming initial “off” time in both groups to be 5.1 hours, a decrease in “off” time of 2 hours in the rifaximin group, and no change in the placebo group, we will have 87.7% power or 64.9% power to detect the difference between groups based on standard deviations of 1.5 and 2.0 hours, respectively. Due to the nature of this pilot study, and the imprecise estimates of standard deviation, it is possible that this analysis will not have the power to detect a treatment difference between groups. However, these data will provide valuable estimates of mean and standard deviation which can be used

to design a larger clinical trial. Furthermore, the within-subjects analysis described above should have ample power to detect a treatment effect.

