We expect some people to be identified as having SIBO using serum unconjugated bile acids only, some to be identified using breath tests only, and others to test positive by both methods. To determine whether treatment effect varies by detection method, we will compare the change in “off” time at one month after the start of treatment in the three groups using a one-way ANOVA.

All power estimations were made using PROC POWER in SAS 9.3. The generation of codes for randomization and all the analyses will also be conducted using SAS 9.3.

Treatment of missing data will be handled on a case-by-case basis. The pilot nature and modest sample size of this study makes imputation not appropriate. The decision to exclude a single missing value, series of longitudinal values for a patient, or a patient’s entire data set will vary depending on time of drop-out (if applicable) and type of missing data.

Strategies to mitigate potential pitfalls: To avoid normal day-to-day PD-associated variability to substantially alter the “off” and “on” diary outcomes, we will conduct all measurements at the same time of day in each subject. Also, we do anticipate a number of early drop-outs due to inability to comply with the extensive set of study-related procedures. This might pre-select more motivated patients and bias recruitment in favor of those willing and able to invest the time and effort. However, it is likely these subjects will have an “off” time substantially above that of the inclusion cutoff, thus increasing the range of effect by rifaximin. Finally, SIBO measurements have not been previously applied to PD patients. We will closely monitor for quality metrics and patient adherence given the unique features of the PD population compared to patients with primary GI disorders.

Next steps: Data gathered in this study will inform the design of a large, definitive NIH-sponsored study on the value of rifaximin as a promising management strategy in the care of patients with PD.

Data Storage and Confidentiality: All records from this study will be maintained in a secure setting. Electronic records will be stored on a password protected computer. Records will not have any patient health information (PHI) associated with them. These records will be kept indefinitely to allow for re-analysis of data, if needed. The data will be verified by multiple members of the research team, including the PI. The data will never be accessible without a secured password.

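### The only placebo-controlled test of 'off' time does not say whether baseline is ignored or subtracted, and no baseline covariate is planned

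*Combined protocol and SAP*

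**What the plan says.** All places are in the combined protocol and SAP.

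- **Outcome.** Under Hypothesis and Specific Aims, the primary endpoints are set "to determine the change in “off” time after rifaximin treatment". The statistical analysis section agrees: "Our primary outcome, change in “off” time, will be analyzed using two separate analyses". One of the two is a paired t-test, the other a two-sample t-test.
- **Between-group test.** The sentence that specifies the two-sample test is about follow-up values: "We will use a two-sample t-test to compare the “off” time between groups A and B at 1 month and 3 months past baseline". The primary endpoints paragraph has similar wording for 'off' time: "time will be compared using a between-subjects analysis (rifaximin versus placebo").
- **Contrast.** For the ANOVA by detection method, the same section does write change: "we will compare the change in “off” time at one month after the start of treatment".
- **Role of the test.** The between-group comparison is described as "a second analysis with greater validity for designing a future placebo-controlled trial". The plan also concedes that "it is possible that this analysis will not have the power to detect a treatment difference between groups".
- **Power.** The stated figures are 87.7% and 64.9% for SD 1.5 and 2.0 h. They start from "Assuming initial “off” time in both groups to be 5.1 hours", with a 2 h fall on rifaximin and none on placebo.
- **Entry rule.** The Study Plan and the Inclusion criteria require a baseline diary average of at least 4 h of 'off' time per day.

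**The concern.** The paired test and the ANOVA have no placebo comparison, so group A against group B is the only placebo-controlled test of 'off' time. Two analysts could read the plan differently: one would test follow-up values, the other change from baseline. With 12 patients per group the two can give different answers, and the text does not settle which applies.

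Neither reading makes best use of the baseline diary and Kinesia data, which are collected anyway. A raw comparison carries part of any chance baseline imbalance into the estimate. A change score over-corrects when the before-after correlation is low. The plan relies on this comparison to design the next trial and already doubts its power. The power sentence also takes no account of the 4 h entry rule.

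**Working it through.** **Inputs from the plan:** 12 per group; difference 2 h; mean 5.1 h; SD 1.5 and 2.0 h (between-group test); SD 2.5 h with correlation 0.7 (paired test); entry at 4 h or more.

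**Assumptions:** two-sided alpha 0.05, which the plan does not state; correlations of 0.3 and 0.5 added to the plan's 0.7; baseline and follow-up bivariate normal with equal SDs before the entry cut; constant 2 h effect. The figures are for the diary only, because the plan gives no SD or correlation for Kinesia.

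**Step 1: reproduce the plan.** Two-sample noncentral t, 22 df, noncentrality 2 / (SD × √(2/12)):
- SD 1.5 h: 3.27, power 87.7%
- SD 2.0 h: 2.45, power 64.9%
- SD 2.5 h: 1.96, power 46.6%

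For the paired test, the SD of the difference is 2.5 × √(2 × 0.3) = 1.94 h. With n = 24 this gives 99.8% for 2 h and 95.3% for 1.5 h. All four stated figures reproduce, which supports the inferred alpha.

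**Step 2: do the power figures settle the reading?** The SD of change is SD × √(2(1 − r)), which equals SD at r = 0.5. So 87.7% and 64.9% arise from raw values, from change scores at correlation 0.5, or at any correlation if 1.5 and 2.0 h are themselves SDs of change. They do not settle it.

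**Step 3: effect of the entry rule.** With mean 5.1 h and SD 2.0 h, (4 − 5.1)/2.0 = −0.55, so 29% of patients lie below 4 h. Two settings were used:
- *Setting 1:* mean 5.1 h before the cut. Enrolled mean is 6.07 h and baseline SD 1.41 h.
- *Setting 2:* mean before the cut lowered (to 2.24 h at SD 2.0 h) so that enrolled patients average 5.1 h. Baseline SD is 0.92 h.

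**Step 4: power by simulation.** 300,000 trials per cell; t-tests on 22 df, ANCOVA on 21 df, with baseline random so that chance imbalance is costed. Entries are raw / change / ANCOVA, in %, with r taken before the cut.

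| Setting, SD | r = 0.3 | r = 0.5 | r = 0.7 |
|---|---|---|---|
| 1, 1.5 h | 89.0 / 81.9 / 89.0 | 91.2 / 91.3 / 93.9 | 94.2 / 98.6 / 98.8 |
| 1, 2.0 h | 66.9 / 58.7 / 66.8 | 70.7 / 70.6 / 74.9 | 77.0 / 88.2 / 89.1 |
| 1, 2.5 h | 48.4 / 41.9 / 48.3 | 52.1 / 52.1 / 56.1 | 58.6 / 71.2 / 72.4 |
| 2, 1.5 h | 89.7 / 85.5 / 89.0 | 92.8 / 92.8 / 93.8 | 96.8 / 98.9 / 98.8 |
| 2, 2.0 h | 68.0 / 64.1 / 66.6 | 74.3 / 74.4 / 75.1 | 84.7 / 89.5 / 89.1 |
| 2, 2.5 h | 49.5 / 47.1 / 48.1 | 56.0 / 55.9 / 55.9 | 68.8 / 73.4 / 72.3 |

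At SD 2.0 h, ANCOVA minus raw is about 0/+4/+12 points in setting 1 and −1/+1/+4 in setting 2. Change minus raw is −8/0/+11 and −4/0/+5.

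Over the grid, ANCOVA's largest shortfall against the better t-test is 68.0 − 66.6 = 1.4 points. Its largest gain over the worse is 72.4 − 58.6 = 13.8 points.

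**Step 5: bounds.** With no cut at SD 2.0 h, raw is 64.9%, change 50.8/64.9/85.6% and ANCOVA 66.8/75.0/89.0%. At r = 0 with the cut, ANCOVA gives 62.6% against 64.7% raw.

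**Step 6: chance imbalance.** The SE of the baseline difference is baseline SD × √(2/12): 1.41 h gives 0.58 h and 0.92 h gives 0.38 h. A raw comparison carries r times this into the estimate: 0.17/0.29/0.40 h, or 0.11/0.19/0.26 h, against a 2 h effect.

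**The case against.** The strongest reply is that a change-score test is at least as natural a reading, because the section opens by naming change as the outcome. Against that test ANCOVA gains little on the plan's only stated SD and correlation pair (2.5 h, 0.7): 72.4 − 71.2 = +1.2 points in setting 1 and 72.3 − 73.4 = −1.1 in setting 2. The +12 pairs SD 2.0 h with correlation 0.7, which the plan never does. The quoted SDs may also already be SDs of change. Taking 2.0 h that way with correlation 0.7 and the entry cut, change against ANCOVA is 68.6 against 69.8% in setting 1 and 70.9 against 69.7% in setting 2. All of this stands, and it means the size of the gain is uncertain. It does not remove the ambiguity: on the same 2.5 h and 0.7 pair, the literal wording gives 58.6% or 68.8%.

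The two settings also strain the plan's inputs. Setting 2 makes only 19% of patients eligible and has the untreated placebo mean fall from 5.1 h to 3.1/3.7/4.2 h. In setting 1 it falls from 6.07 h to 5.39/5.58/5.78 h. The plan assumes no change on placebo. Setting 2 is best read as a lower bound. If SD 2.0 h and the correlation describe enrolled patients, as the plan's 64.9% treats the SD, the gain over the raw test is larger, about +2/+10/+24 points.

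Finally, this is a pilot that admits low power, and both t-tests are valid. That is why the point is not put as bias. It is no reason to leave the test open, since chance imbalance matters more with small groups.

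**Conclusion.** The concern holds. The wording gap is certain: the outcome is change, the specified test is on follow-up values, and no baseline covariate appears. The power gain from ANCOVA depends on the correlation. At SD 2.0 h with the entry rule it is about 0/+4/+12 points over the raw test at 0.3/0.5/0.7, or −1/+1/+4 if enrolled patients average 5.1 h. At low correlation the gain is nil or slightly negative, and the case then rests on pre-specification and on handling chance imbalance. The firmest argument is robustness: for SD 1.5 to 2.5 h and correlations of 0.3 to 0.7, ANCOVA is at most about 1.5 points below the better t-test and up to 14 above the worse. These figures assume normality, a constant 2 h effect, no dropout and two-sided alpha 0.05. The plan should be changed, but the flaw does not invalidate the trial.

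**What to change.** Before unblinding:

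1. Reconcile the outcome wording with the test.
2. Pre-specify that 'off' time at month 1 and at month 3 is compared between groups A and B by ANCOVA, with baseline-visit 'off' time as covariate, for the diary and for Kinesia. A single repeated-measures model with the same covariate could serve instead, but one must be named; its power was not evaluated here.
3. Report the adjusted difference with its 95% confidence interval, together with the SD at each visit and the before-after correlation among enrolled patients, for use in sizing the next trial.
4. Restate between-group power with its alpha for SD 1.5, 2.0 and 2.5 h over a range of correlations, allowing for the 4 h entry rule and stating the mean 'off' time expected in enrolled patients.

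The cost is one degree of freedom and some redrafting, since the baseline diary and Kinesia data are already collected. If baseline proved unrelated to follow-up, the loss would be about 2 power points at SD 2.0 h. At correlation 0.3 with an enrolled mean of 5.1 h it would be about 1 point against the raw test.

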2. **To compare outcomes of the Hauser diary versus the Kinesia 360 monitoring system.** Within-patient results will be compared for sensitivity and effect size, and these data will be used to select the primary endpoint for a larger, randomized trial.

Tertiary endpoints:

1. Change in daily “on” time with no dyskinesia and without troublesome dyskinesia.
2. Change in daily “on” time with troublesome dyskinesia
3. Change in motor subscale (part III) of the Movement Disorders Society-Unified Parkinson's Disease Rating Scale (MDS-UPDRS)
4. Change in the complication of therapy subscale (Part IV) scores of the MDS-UPDRS
5. Presence/recurrence of SIBO 1 month post-treatment
6. Correlation between the treatment effect of rifaximin (change in “off” time) and SIBO eradication as measured by both non-invasive methods of SIBO detection.
7. Change in Patient Global Impression of Change (PGI-C).

The current proposal is designed to demonstrate our ability to detect and treat SIBO in PD patients with motor fluctuations, to estimate the effect size and standard deviation of motor improvements, and to inform selection of the best SIBO detection method. In addition, it will help us determine the optimal timeline for assessing motor endpoints, and estimate the duration of benefits after treatment.

BACKGROUND AND SIGNIFICANCE

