Study Plan: PD patients with motor fluctuations (≥ 4 hours of self-reported "off" time per day) will be screened for SIBO using breath tests (LBT and GBT). Subjects testing positive by either method will be eligible for enrollment, whereas those testing negative by *both* methods will be considered screen failures, and will be discontinued from the study. We expect that approximately 50% of screened patients will be SIBO-positive [1, 2]; therefore we plan to screen 48 subjects to achieve an enrollment of 24. SIBO-positive subjects will be asked to return for a baseline visit 2-4 weeks after screening, and to complete the standardized Hauser diary[16, 17] capturing daily "on" and "off" time for 3 days prior to the baseline visit. Daily "off" time must average at least 4 hours per day to proceed with enrollment. They will also use the Kinesia 360 monitoring system during this time.

Subjects meeting all inclusion/exclusion criteria will be enrolled and randomly assigned to one of two groups in a randomized, double-blind, crossover fashion (see Figure), each treated with a one-week course of the antibiotic rifaximin as well as a one-week course of matching placebo. Group A will receive rifaximin at baseline and placebo at 3 months, whereas group B will receive placebo at baseline and

rifaximin at 3 months. Outcome measures including motor control will be assessed at the following time points: baseline (BL, pre-treatment), 1 month, 3 months, 4 months, and 6 months.

Clinical assessments will include a motor examination and evaluation of motor complications using sections III and IV of the MDS-UPDRS, respectively. Patients will be trained in the correct use of the PD Hauser diary to log “on” and “off” time, as described below.

Blinding: Amendment 3 modifies this study to be a fully double-blind crossover, such that neither participants nor researchers will know when the subject receives rifaximin or placebo. This will be explained to the participants, so they will know that they will receive one treatment course of each during the study, but they will not know in which order they were treated. The results of the breath tests (SIBO-positive or SIBO-negative) will only be revealed to the subject at screening, which determines their ability to enroll in the study. The results of subsequent breath tests on enrolled subjects will not be revealed to subjects or the motor assessor to avoid bias on symptomatic outcome measures.

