Breath Tests: GBT and LBT will be performed according to standard procedures on separate days. Subjects are placed on a restricted, low-carbohydrate diet the day before the test, and fast for 12 hours prior to GBT and LBT. A baseline alveolar air sample will be collected before ingestion of glucose (1g/kg of body weight) or lactulose (10g), followed by sampling every 20 minutes for 3 hours. The diagnosis of SIBO is established by expert review by an experienced Gastroenterologist. Generally, a positive GBT is defined as an increase in exhaled hydrogen ≥ 10 parts per million above baseline. A positive LBT is characterized by two distinguishable hydrogen peaks (SIBO and colonic peaks) after lactulose ingestion [19]. However, individual variances in hydrogen dynamics require expert review for a final determination.

- Screening breath tests (LBT and GBT) that do not exhibit a rise in hydrogen levels of at least 8 ppm in the first 80 minutes will be discontinued and considered negative. All others will be completed for later determination.
- After screening, all enrolled subjects will have breath tests performed to completion to avoid revealing the results of the test to the participant.

Measurement of Serum Unconjugated Bile Acids: Serum will be obtained from subjects in order to measure concentration and fractionation of UBA. Batched samples will be analyzed in a post-hoc fashion, and not used for screening (study inclusion) purposes. The major primary and secondary unconjugated and conjugated bile acids will be measured in serum using a routine validated LC-MS/MS method according to CCHMC SOP # PATH.CMS.1033.

Study Drug and Placebo: Rifaximin treatment will be a 7-day course of 550mg three times per day (1650mg/day). The drug is supplied as 550mg tablets. Matching placebo tablets will be administered in the same fashion.

PD Diary: Patients will be instructed to use the Hauser diary [16] to log their motor fluctuations for three consecutive days prior to each study visit (concurrent with Kinesia monitoring). Each diary page is a grid representing a 24-hour day in which patients mark each half-hour period as one of 5 categories: Asleep, OFF, ON without dyskinesia, ON with non-troublesome dyskinesia, or ON with troublesome dyskinesia.

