Kinesia 360 Monitoring. Kinesia is an FDA cleared to market device for objectively assessing Parkinson’s disease symptom severity. The system includes wireless motion sensors and a tablet PC. Subjects will be trained in its use at screening, and will use it for 3 consecutive days prior to each subsequent study visit (concurrent with PD diary completion).

MDS-UPDRS On/off evaluation: The MDS-UPDRS part III (motor examination) will be used to evaluate subjects in both the “on” and “off” conditions. MDS-UPDRS part IV (motor complications) is an interview-based assessment that refers to the subject’s functioning over the past week, and thus can be conducted in either the “on” or “off” state. These will be completed at all study visits except screening. The “off”

portion will be conducted after subjects have abstained from PD medications for 12 hours. Following motor evaluation, they will take their normal dose of PD medication(s), and will be evaluated again one hour later, or when the subject reports feeling fully “on”.

Patient Global Impression of Change. The subject will rate his/her impression of change in PD symptoms from baseline (i.e., just before subject’s most recent study drug treatment) to the time of assessment. The PGI-C is assessed on a 7-point scale ranging from “very much improved” to “very much worse”.

Screen Failures and Rescreening:

Subjects whose breath tests are negative will be considered screen failures and will not be enrolled in the study. However, bacterial populations in the intestine may change with diet, antibiotic treatment, or other conditions. For these reasons, the investigator and subject may elect re-screening following negative results. Elective rescreening following two negative breath tests must be at least 14 days after previous breath testing.

In other cases, breath test results may be borderline, incomplete, or otherwise undetermined as deemed by expert review. These subjects may return for rescreening 1-60 days following previous breath testing. At minimum, the previously-undetermined breath test (GBT or LBT) must be repeated. Both breath tests may be repeated at investigator discretion. If more than 60 days have passed following breath testing, then both GBT and LBT must be completed.

Randomization, Sample Size Estimation and Statistical Analysis Plan: PD patients testing positive for SIBO will be randomized to group A or B in equal numbers using a randomization code generated by the statistician.

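### The bile-acids-only group is empty under the enrolment rule, so the three-group ANOVA for secondary endpoint 1 cannot support a choice between bile acids and breath tests

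*Combined protocol and SAP*

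**What the plan says.** - **Purpose.** Secondary endpoint 1 (Hypothesis and Specific Aims) sets UBA against the combined breath tests and undertakes to "use these data to select the detection method for a larger, randomized trial".
- **Who is enrolled.** Study Plan, after naming the lactulose and glucose breath tests (LBT and GBT) as the screening tests: "Subjects testing positive by either method will be eligible for enrollment". Those negative on both are discontinued. Screen Failures and Rescreening repeats this: "Subjects whose breath tests are negative will be considered screen failures and will not be enrolled in the study".
- **Role of UBA.** Measurement of Serum Unconjugated Bile Acids: "Batched samples will be analyzed in a post-hoc fashion, and not used for screening (study inclusion) purposes".
- **Numbers.** Study Plan expects about half of those screened to be positive, "therefore we plan to screen 48 subjects to achieve an enrollment of 24".
- **Analysis.** The statistical analysis plan states "We expect some people to be identified as having SIBO using serum unconjugated bile acids only", expects a breath-only and a both-positive group as well, and compares off-time change "at one month after the start of treatment in the three groups using a one-way ANOVA".
- **Related endpoint.** Tertiary endpoint 6 correlates the treatment effect with "SIBO eradication as measured by both non-invasive methods of SIBO detection".

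**The concern.** The analysis needs a group that the enrolment rule excludes. A patient positive on UBA alone is breath-negative, so is a screen failure, receives no study treatment and has no post-rifaximin off-time to analyse. What is left is a comparison within breath-positive patients, which answers a different question from the one endpoint 1 poses.

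The choice of detection method for the larger trial is a stated deliverable of this pilot. To choose UBA over or against breath tests, one has to know how the patients each method would admit respond, and those admitted by UBA alone are not studied. If the ANOVA result were read as a comparison of methods, the next trial's entry criterion could rest on evidence that does not bear on it.

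**Working it through.** **Step 1. Group membership.** Every enrolled subject is LBT-positive or GBT-positive at screening. Cross-classifying by UBA gives:

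| Screening status | Enrolled? | Planned ANOVA group |
|---|---|---|
| Breath+, UBA+ | yes | both methods |
| Breath+, UBA− | yes | breath only |
| Breath−, UBA+ | no | UBA only: n = 0 |
| Breath−, UBA− | no | none |

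With 24 subjects, three groups would give df 2 and 24 − 3 = 21; two groups give df 1 and 24 − 2 = 22. On the plan's expectation, about 48 − 24 = 24 screened patients are breath-negative, and any UBA-only patient is among them. Rescreening does not change this, since entry still requires a positive breath test.

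**Step 2. Check of the inputs.** The plan gives no power for this analysis, so I first reproduced its primary-outcome figures (noncentral t; two-sided 5% assumed, as alpha is not stated).
- Paired, n = 24, SD 2.5 h, r = 0.7: SD of change = 2.5 × √(2 × (1 − 0.7)) = 1.936 h. Power is 99.8% for 2 h and 95.3% for 1.5 h, as stated.
- Two-sample, 12 per group, 2 h: 87.7% at SD 1.5 h and 64.9% at SD 2.0 h, as stated.

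**Step 3. What the two-group contrast can deliver.** SD of change = SD × √0.6. CI half-width = t(0.975, 22) × SD of change × √(1/n₁ + 1/n₂), with t = 2.074. For example, at SD 2.5 h and 12:12: 2.074 × 1.936 × √(1/12 + 1/12) = 1.64 h. The UBA split is not in the documents; 12:12 and 18:6 are assumptions.

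| SD (h) | SD of change (h) | Half-width 12:12 (h) | Half-width 18:6 (h) | Power for 2 h, 12:12 | Power for 2 h, 18:6 |
|---|---|---|---|---|---|
| 1.5 | 1.16 | 0.98 | 1.14 | 98.1% | 93.7% |
| 2.0 | 1.55 | 1.31 | 1.51 | 85.6% | 74.5% |
| 2.5 | 1.94 | 1.64 | 1.89 | 67.7% | 55.4% |

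A 2 h gap between subgroups equals the whole rifaximin effect the plan assumes, so these powers are optimistic. For a 1 h gap at 12:12, power is 52.2%, 32.7% and 22.7% at the three SDs. No dropout is allowed for.

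**Step 4. Does another endpoint fill the gap?** Tertiary endpoint 6 uses both detection methods, but in the same subjects, all breath-positive at screening. It does not.

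**The case against.** The strongest reply is that the plan does not say which visit defines detection status. Breath tests are repeated after enrolment, and group B's pre-rifaximin point is month 3. If status were taken just before rifaximin, a subject could be breath-negative and UBA-positive, and three groups could exist. That is correct, and it is why the finding is limited to screening status. It does not rescue the endpoint: any such subject was breath-positive at screening, so patients whom UBA would find and breath tests would miss are still absent.

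Second, the two-group contrast has some use for method selection, because it bears on breath tests alone against breath tests with UBA confirmation. This stands. What is lost is UBA as a stand-alone or competing selector.

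Third, a UBA cut-off may be in the cited laboratory SOP, and sampling visits may be in the study figure; neither is available here. So it can be said only that the text gives neither a UBA threshold nor a defining visit, though it gives general criteria for both breath tests.

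Fourth, the 24 breath-negative patients are an approximation. Some may be rescreened and enrolled after a later positive test, and some breath-positive patients will fail the diary criterion. The zero in the UBA-only group does not depend on that count.

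**Conclusion.** The concern holds. On screening status the UBA-only group is empty by rule (0 of 24), the three-group ANOVA becomes a two-group test, and that test cannot deliver the choice between UBA and breath tests that endpoint 1 promises. This follows from the plan's own enrolment rule and needs no outside figure. The precision figures for the remaining contrast rest on the plan's SDs and its correlation of 0.7, and on assumed UBA splits, a two-sided 5% level and complete data. This should be fixed, but it is confined to a secondary endpoint.

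**What to change.** Reconcile secondary endpoint 1, Study Plan, the UBA measurement paragraph, Screen Failures and Rescreening, and the detection-method paragraph of the analysis plan.

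1. Replace the three-group ANOVA with a two-group comparison of off-time change by UBA status at screening or baseline. Fix the UBA threshold and the defining visit before unblinding, and report the difference with a 95% CI as an estimate.
2. Reword endpoint 1 as whether UBA status modifies the response to rifaximin among breath-test-positive patients. State that UBA-only patients are not studied and that UBA cannot be judged as a stand-alone selector from these data.
3. Optional, and a separate matter: raw before-after change also contains placebo response and regression to the mean, so a placebo-adjusted UBA-by-treatment estimate could be added as supportive. State whether it uses the first period only, or both periods, which assumes no carryover of rifaximin into group A's placebo period.

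**Cost.** Items 1 and 2 change one endpoint and one analysis paragraph. They need no new data provided a pre-treatment serum sample exists; the text does not say when serum is drawn. The price is a narrower claim about UBA and wide intervals. Item 3 is imprecise. For SDs of 1.5 to 2.5 h at 12:12, its half-width is 1.39 to 2.32 h using both periods (the two changes taken as uncorrelated; power for 2 h 81.3% to 40.2%). Using the first period alone with 6 per cell, it is 1.98 to 3.30 h (power 51.9% to 22.6%).
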